- 7. For clarification purposes, going forward "Phase 1" will be used to describe the interview and medical record information collected during pregnancy and, for infants, until they are 4 months of age. "Phase 2" will be used to describe the interview and medical record information collected from participants of Phase 1 through 15 months following the end of the pregnancy.
- 8. The registry name is updated throughout to the COVID-19 Vaccine Pregnancy Registry.

Background:

Pregnancy was an exclusion from enrollment in pre-EUA clinical trials for COVID-19 vaccines (www.clinicaltrials.gov). In these pre-EUA clinical trials, pregnancy was screened for and pregnant persons were excluded based on positive urine pregnancy tests; clinical trial participants were recommended to avoid pregnancy during the trial by using reliable and effective contraception. While Pfizer and Moderna vaccine trials did include approximately 36 pregnant persons inadvertently vaccinated during pregnancy, these small numbers are not enough to establish the safety of maternal vaccination (1, 2). Safety data from infants exposed during pregnancy is not available because of the short length of follow up.

On December 1, 2020, the Advisory Committee on Immunization Practices (ACIP) voted that, when a COVID-19 vaccine is authorized by the FDA and recommended by ACIP, healthcare personnel should be offered vaccination in the initial phase of the COVID-19 vaccination program (phase 1a) (3). The healthcare workforce is predominantly female, and women account for 75% of full-time year-round healthcare personnel (4). Females also dominate the largest healthcare occupations, comprising 88% of registered nurses and 86% of healthcare support workers, which includes nursing, psychiatric, and personal and home health aides. Approximately 5% of women of reproductive age are estimated to be pregnant or postpartum at any time, translating to around 330,000 pregnant or newly postpartum women who are healthcare personnel and could be included in phase 1a vaccine allocation. Furthermore, on December 20, 2020, the ACIP voted that phase 1c vaccine allocation includes persons aged 16-64 years with medical conditions that increase the risk for severe COVID-19, of which pregnancy is included (5).

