3b. To monitor infant COVID-19 vaccination and characterize participant-report of infant adverse effects following COVID-19 vaccination

Objective 4: Among persons who received COVID-19 vaccination during pregnancy, evaluate risks for pregnancyrelated medical conditions, including thromboembolic events, as well as new autoimmune conditions, and heart conditions, in the first 15 months postpartum.

Methods:

Surveillance Population and Inclusion Criteria

The population of pregnant persons eligible for surveillance through the pregnancy registry will include those exposed to COVID-19 vaccines during pregnancy or in the periconception period (30 days before LMP through 14 days after LMP) (Figure 1). Additional data will be collected on these pregnant persons; infants born to these persons will be monitored for the first 15 months of life to identify any newborn and infant complications and diagnoses of major birth defects. Persons who are found not to be pregnant at the time of vaccination and are not identified as pregnant within 30 days after vaccination will not be included in the registry. There may be participants who are initially determined to be eligible based on their reported LMP during the first interview

but may later be deemed to be ineligible if gestational age estimation is updated over the course of pregnancy. These participants will be excluded from outcome analyses and the 15-month follow-up survey (n=70).

Identification of exposed pregnancies

The v-safe After Vaccination Health Checker system is an opt-in text messaging and web-based surveillance system that is offered to COVID-19 vaccine recipients. As part of the initial v-safe survey, all non-male participants (i.e., female, prefer not to say, other) will be asked questions about pregnancy status. In addition, screening questions to identify potential pregnancies will be asked at v-safe health check-ins that occur at days 21 and 42 after each vaccine dose (if applicable) and at 3, 6, and 12 months after the last vaccine dose (Figure 2). V-safe data managers at CDC will notify the pregnancy call center team (described below) of potential pregnant vaccine recipients. The pregnancy call center will be staffed by individuals trained to administer the questionnaire and on the handling of PII. To identify as many pregnant persons as possible through v-safe, the follow up plan is:

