- If a person answered "yes" to any pregnancy question, on the v-safe text messaging survey, they were sent a follow-up survey by Oracle to respond to three questions. The first question confirmed pregnancy and the other two questions were related to interest in participating in the pregnancy registry. All survey responses were-sent to the pregnancy call center.
- Those who responded "yes" to any pregnancy question, "yes" to being interested in the follow-up survey or who did not respond at all were contacted by the pregnancy call center. During the initial call, the pregnant person was asked if they would like to participate in the pregnancy registry. If they declined, there was no further contact by the pregnancy call center. They remained enrolled in the v-safe text message monitoring system unless they replied with "STOP" to opt out.
- If they no longer participated in the v-safe survey questions (i.e., stopped responding or opted out) after indicating "don't know" to a pregnancy question, they were contacted by the pregnancy call center within 3 months of their last response to inquire about their pregnancy status.

The CDC COVID-19 Vaccine Pregnancy Registry call center staff were notified of participants who might be pregnant via a dataset that was created from the v-safe After Vaccination Health Checker system. The dataset includes the following variables:

- Unique v-safe ID
- First Name
- Last Name
- Sex
- Full date of birth
- Phone Number
- Zip code
- Time zone
- Preferred language
- Race/ethnicity
- Vaccination dates
- Vaccine type
- Pregnancy response date
- Survey number that identified pregnancy

Data collection:

CDC pregnancy call center and registry

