
The initial contact will collect pregnancy history information, including outcomes of prior pregnancies, the gestational dating of the vaccine-exposed pregnancy, and pregnancy and postpartum complications or comorbidities. Previously, call center follow-up interviews occurred once every trimester to identify any pregnancy complications, and a follow-up interview occurred at 4-8 weeks postpartum to obtain information on the delivery, any potential complications in the participant or infant, and to request consent from the participant for release of her and the infant's medical records. By the end of February 2022, all pregnancies reported to v-safe that were included in the pool of potential pregnancy registry participants had ended by the time of initial contact. This was due to resource constraints and the fact that the estimated due date for the pregnancy reported to v-safe was unknown prior to the initial outreach from the pregnancy registry call center. Therefore, for over half of enrolled registry participants, all information about the pregnancy and outcome was collected at the time of the registry's initial outreach. A brief call center follow-up interview occurred when the infant was 3 months old to inquire about any adverse events, including the diagnosis of any birth defects. If the initial call occurred when the infant was older than 3 months old, this information was obtained at the initial call as well. Finally, in the 2nd phase of the registry, focused on the participants' and infants' health in the year following the end of the pregnancy, a single interview will be conducted for the time period through 15 months following the end of the pregnancy. This interview will be administered, when the infant is at least 16 months old to ensure a consistent amount of time has passed since delivery. Participants will be asked about their health status as well as their infant's, including any birth defect diagnoses, infant medical conditions, COVID-19 infections, and hospitalizations, during that 15-month period. Participants who experienced a pregnancy

outcome other than a live birth (e.g., stillbirth, spontaneous abortion, induced abortion, ectopic pregnancy) or have already shared that their infant is deceased will only be asked the set of questions about maternal health. Participants whose pregnancy outcome is not yet known at the time of the 15-month interview will additionally be asked questions about their pregnancy outcome.

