Ongoing data quality checks occur to identify errors, including implausible and missing values. Data from the pregnancy registry are analyzed monthly at minimum. Reports include descriptive analyses of any adverse outcomes and rates of follow up among pregnant persons. Specifically, rates are calculated for fetal demise (spontaneous abortion and stillbirth), pregnancy complications (pregnancy induced hypertension, gestational diabetes, pre-eclampsia), adverse birth outcomes (preterm delivery, small for gestational age, low birth weight, neonatal intensive care unit stays), major birth defects, and other outcomes of interest. These proportions may be compared to national averages, published background rates or estimates seen in other data systems with similar demographics. For outcomes that may undergo clinical review and adjudication, sensitivity analyses will be performed that account for any potential recategorization of outcomes following the clinical adjudication processes (clinical review of participant-reported data and/or medical record data by clinical SMEs). Adverse events may be analyzed in aggregate if rare (i.e., any major cardiac defect). Any potential safety signals will be compared to other surveillance systems, such as VAERS, and specifically for birth defects, the CDC's Metropolitan Atlanta Congenital Defects Program or the Texas Birth Defects Registry (19, 20). Persistent signals will be evaluated using more robust surveillance system data (such as the Vaccine Safety Datalink) that have denominator data of pregnant persons who received COVID-19 vaccines and comparison groups of pregnant persons who did not receive COVID-19 vaccines. For rare outcomes, evaluations may also be conducted in other database systems, such as the FDA or the Department of Defense (DOD), for appropriate follow up assessment.

Because we do not have a control group and the pregnancy registry is not nationally-representative, we will compare characteristics of pregnancy registry participants with those of representative samples of pregnant people within the United States to aid in the interpretation of generalizability. For example, we may compare the outcomes with already collected data from other surveillance systems, such as the Pregnancy Risk Assessment Monitoring System or Vaccine Safety Datalink or compare to background rates in the literature.

Outcomes:

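### Complication rates may be set against background rates with no rule that onset follows the dose, so a real vaccine effect would be diluted

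*Protocol*

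**What the plan says.** The Analysis plan lists, among the rates to be calculated, "pregnancy complications (pregnancy induced hypertension, gestational diabetes, pre-eclampsia". Of the listed rates it says: "These proportions may be compared to national averages, published background rates or estimates seen in other data systems with similar demographics". The comparison has to be external, and the same section gives the reason: "Because we do not have a control group".

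Under Surveillance Population and Inclusion Criteria, the eligible population is "those exposed to COVID-19 vaccines during pregnancy or in the periconception period (30 days before LMP through 14 days after LMP". A first eligible dose can therefore fall at any gestational age. No section says that onset of these three conditions must follow the dose, defines a group free of the condition at the dose, or splits these rates by gestational age at dose. Objective 4, by contrast, does address timing: it asks for new autoimmune conditions and sets a postpartum window.

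On the data held, the file passed to the call center includes "Vaccination dates", and the first interview records LMP and gestational dating. Complications are collected, but no onset date is mentioned. The Data collection section adds that for over half of enrolled participants "all information about the pregnancy and outcome was collected at the time of the" registry's first contact.

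The Limitations section commits to a sensitivity analysis confined to people enrolled and followed before an adverse pregnancy or birth outcome.

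**The concern.** A case that began before the dose cannot have been caused by it. It adds to the registry rate just as it adds to the background rate, so the observed ratio becomes a weighted average of 1 and the true ratio.

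These conditions differ from pregnancy loss in that they do not end the pregnancy. A person can be diagnosed, be vaccinated later and still qualify. Someone diagnosed with gestational diabetes at 26 weeks and first dosed at 34 weeks would count as a complication in an exposed pregnancy. Correcting denominators for miscarriage or preterm birth does not remove such a case.

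What is at stake is a missed signal. The Analysis plan sends persistent signals on to systems that have unvaccinated comparison groups. An effect diluted at the first step may never be sent.

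**Working it through.** The protocol states no rate, effect size or share of pre-dose cases for these outcomes, so there is no figure of its own to reproduce. What follows is an illustration. The exposure window and the dates come from the protocol; everything else is labelled as assumed.

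**Are late doses real?** The Background shows that authorization was still to come on 1 December 2020. The Data collection section says that calls start in November 2022 and that 17% of eligible participants will by then be more than 19 months past their outcome, so their pregnancies ended before about April 2021. From 1 December 2020 to 1 or 30 April 2021 is 121 or 150 days. A birth at 40 weeks (assumed) in that group was first dosed no earlier than (280 − 150)/7 = 18.6 to (280 − 121)/7 = 22.7 weeks. Known live births make up 92% of eligible pregnancies. Even if the other 8% all fell in this group, about 17 − 8 = 9% of participants would be live births from it. Late doses therefore did occur.

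**Share of cases that predate the dose.** Assume first doses are spread evenly from 30 days before LMP to 40 weeks, which is 30 + 280 = 310 days. The share dosed after week w is f = (280 − 7w)/310. If a condition is diagnosed at week w, f is also the share of background cases that predate the dose.

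- w = 20: 140/310 = 0.45
- w = 24: 112/310 = 0.36
- w = 28: 84/310 = 0.27

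**Dilution.** If a diagnosis does not affect vaccination, the observed ratio is f + (1 − f) × RR. For RR = 1.5:

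- Gestational diabetes, diagnosis assumed at 24 to 28 weeks: 0.361 + 0.639 × 1.5 = 1.32, and 0.271 + 0.729 × 1.5 = 1.36 (1.37 if f is first rounded to 0.27).
- Hypertensive disorders, onset assumed at 20 weeks or later: f is at most 0.45, so the ratio reads at least 0.452 + 0.548 × 1.5 = 1.27. Later onset dilutes less; f = 0.25 gives 1.375 and f = 0.10 gives 1.45.

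**False effect.** With RR = 1 and no link between diagnosis and vaccination, the ratio is f + (1 − f) = 1.00 for every f. Now let k be the relative chance of vaccination once the condition is present, and b the background proportion. The ratio becomes [(1 − f) + fk]/(1 − bf + bfk). With b = 8% and f = 0.25 (both assumed), k = 1.25 gives 1.0625/1.005 = 1.06 and k = 0.75 gives 0.9375/0.995 = 0.94. The bias can run either way, and it needs k to differ from 1.

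**A tempting repair that fails.** Suppose only post-dose diagnoses are counted, among those free of the condition at the dose, while the background stays whole-pregnancy. With no effect the ratio is (1 − f)/(1 − bf). At b = 8% this is 0.73/0.978 = 0.75 for f = 0.27 and 0.64/0.971 = 0.66 for f = 0.36. That is a false protective effect.

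**The case against.** **The protocol is silent; it does not prescribe the error.** No sentence says that pre-dose cases count. Onset rules are often left to a statistical analysis plan, which is not at hand, and clinical review may refine outcome definitions. This stands as a limit on wording: a reader might infer a deliberate rule to count such cases, and the protocol does not support that. The protocol does, however, name the outcomes, the exposure window and the kind of comparator in its own Analysis plan, and these three together give the dilution unless something is added.

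**A sensitivity analysis already exists.** Enrolment follows vaccination, so limiting to people enrolled before the outcome would drop pre-dose cases, if these complications count as adverse pregnancy outcomes. The protocol does not say whether they do. The analysis is also secondary and tied to enrolment rather than to the dose. It discards genuine post-dose cases that arose before enrolment, and it loses many of the participants interviewed only after pregnancy. It is a partial safeguard.

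**A false excess is not shown.** A reader might infer that the rates would show a spurious harm, because the Background describes priority for "persons aged 16-64 years with medical conditions that increase the risk for severe COVID-19, of which pregnancy is included". Pregnancy itself already qualified there, so a further diagnosis added no eligibility under that rule. This objection stands.

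**The analyses are descriptive.** The comparison is optional, and no objective names these three complications. That lowers the weight of the point. Onward evaluation of persistent signals guards against a false excess, but not against an effect that was diluted and never flagged.

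**Conclusion.** The point holds as a dilution problem that is cheap to remove. As written, the comparison with background would understate a real effect on these conditions. For gestational diabetes a true ratio of 1.5 would read about 1.32 to 1.36; for hypertensive disorders it would read no lower than about 1.27. These sizes rest on an assumed even spread of first doses, pregnancies of 40 weeks, and assumed ages at diagnosis. The direction does not depend on those choices, provided some cases predate the dose. Doses given before the condition can begin, such as periconception doses, are unaffected.

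The documents do not support two stronger claims: that the protocol prescribes counting pre-dose cases, and that the rates would show a false harm. The second needs a diagnosis to change the chance of vaccination or enrolment, and nothing in the protocol establishes that.

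**What to change.** In the Analysis plan, state that comparisons of these three complications with background rates are restricted by gestational age at the first eligible dose: before 20 weeks for pregnancy-induced hypertension and pre-eclampsia, and before 24 weeks for gestational diabetes. The vaccination dates and LMP already held are enough to apply this. The cut-offs rest on the assumption that few cases are recorded earlier, which the clinical experts should confirm. Tabulate diagnoses known to predate the dose separately, as baseline conditions. Rates over all registry pregnancies can still be described.

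Where onset dates are held or can be taken from records, incidence after the dose among those free of the condition at the dose may be added. It should be compared only with a background rate for the same gestational window. Otherwise the false protective ratio of about 0.66 to 0.75 shown above would replace the dilution.

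The cost is wording and a smaller denominator. Under the even-spread assumption, 1 − 0.45 = 55% of pregnancies remain for hypertensive disorders and 1 − 0.36 = 64% for gestational diabetes. The true shares would be somewhat higher if pregnancies ending before 40 weeks leave less room for late doses.
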